#### 7.1.5.2. Incomplete Dates

If the onset date of the AE is incomplete and the AE stop date is not prior to the first dosing date of study drug, then the month and year (or year alone if month is not recorded) of onset determine whether an AE is treatment emergent. The event is considered treatment emergent if both of the following 2 criteria are met:

- The AE onset is the same as or after the month and year (or year) of the first dosing date of study drug, and
- The AE onset date is the same as or before the month and year (or year) of the date corresponding to 30 days after the date of the last dose of study drug

An AE with completely missing onset and stop dates, or with the onset date missing and a stop date later than the first dosing date of study drug, will be considered to be treatment emergent. In addition, an AE with the onset date missing and incomplete stop date with the same or later month and year (or year alone if month is not recorded) as the first dosing date of study drug will be considered treatment emergent.

In case when the AE onset date is incomplete and needs to be imputed, the following algorithm will be followed:

- If day is missing but the month and year are available, then the imputed day will be the first day of the month or the first dosing date if they have the same month and year, whichever is later.
- If day and month are missing but year is available, then the imputed day and month will be 01Jan or the first dosing date if they have the same year, whichever is later.

#### 7.1.6. Summaries of Adverse Events and Deaths

The number and percentage of subjects who experienced at least 1 TEAE will be provided and summarized by SOC, PT, and maximum severity as follows:

- All TEAEs
- Grade 3 or higher TEAEs
- ENTO-related TEAEs
- ENTO-related Grade 3 or higher TEAEs
- Serious TEAEs
- ENTO-related Serious TEAEs
- TEAEs leading to ENTO discontinuation

- TEAEs leading to ENTO reductions
- TEAEs leading to ENTO interruptions
- TEAEs leading to death
- TEAEs leading to study discontinuations

A brief, high-level summary of AEs described above will be provided by the number and percentage of subjects who experienced the above AEs. All deaths occurred in the study will also be included.

Multiple events will be counted only once per subject in each summary. Adverse events will be summarized and listed first in alphabetic order of SOC, and then by PT in descending order of total frequency within each SOC. For summaries by severity, the most severe severity will be used for those AEs that occurred more than once in a given subject during the study.

In addition, data listings will be provided for the following:

- All AEs, indicating whether the event is treatment emergent
- All SAEs
- Deaths
- TEAEs leading to ENTO discontinuation

#### **7.1.7. Dose Limiting Toxicity**

Dose limiting toxicity (DLT) will be analyzed based on the DLT analysis set.

A listing of the DLT AEs will be provided by dose level, subject identification, actual dose amount prior to or on the start date of the AE, DLT terms from the investigators, CTCAE terms, and associated severity grade, if available.

#### **7.2. Laboratory Evaluations**

Central laboratory assessment will be used for safety analysis. Laboratory data collected during the study will be analyzed and summarized using both quantitative and qualitative methods. The analysis will be based on values reported in conventional units. When values are below the LOQ, they will be listed as such, and the closest imputed value will be used for the purpose of calculating summary statistics as specified in Section 3.7.

A by-subject listing for laboratory test results will be provided by subject ID number and visit in chronological order for hematology, serum chemistry, and urinalysis separately. Values falling outside of the relevant reference range and/or having a severity grade of 1 or higher on CTCAE severity grade will be flagged in the data listings, as appropriate.

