### **8.6.3. Laboratory Evaluations**

All laboratory data will be listed. Summaries of laboratory data will be based on observed data and will be reported using conventional units. The laboratory data summarization will focus on treatment-emergent laboratory abnormalities. Treatment-emergent laboratory abnormalities are defined as abnormalities that, compared to baseline, worsens by  $\geq 1$  grade in the period from the first dose of study treatment to 30 days after the permanent discontinuation of study treatment. If baseline data are missing, any graded abnormality will be considered as treatment-emergent. Laboratory abnormalities that occur before the first dose of study treatment or  $>30$  days after the permanent discontinuation of study treatment will be included in data listings.

Hematological, serum chemistry, coagulation, and urinalysis data will be programmatically graded according to CTCAE severity grade, when applicable. For parameters for which a CTCAE scale does not exist, reference ranges from the central laboratory will be used to determine programmatically if a laboratory parameter is below, within, or above the normal range based on subjects' age, sex, etc.

Hematological, serum chemistry, coagulation assessments and their changes from baseline will be summarized by presenting the number and percentage of subjects by severity grade. For laboratory tests without CTCAE scale, the summary will present the number and percentage of subjects below, within, and above the normal ranges. Subjects will be counted only once for a given laboratory test under the worst severity grade during a period of interest (eg, during the study or from baseline to a particular visit).

Separate listings and summaries will be prepared for laboratory abnormalities that are  $\geq$  Grade 3.

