#### **7.2.1.2. Summaries of Laboratory Abnormalities**

Summary (number and percentage of subjects) of baseline and worst post-baseline treatment-emergent laboratory abnormalities will be provided by lab test. Subjects will be categorized according to the most severe post-baseline abnormality grade for a given lab test.

A by-subject listing will include all laboratory results with flags to indicate treatment emergent laboratory abnormalities.

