#### **7.7. Changes From Protocol-Specified Safety Analyses**

There are no deviations from the protocol-specified safety analyses.

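### Does the SAP lose laboratory outputs that the protocol promises: Grade 3 or higher tables, coagulation, local results?

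*SAP*

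**What the plan says.** Protocol 8.6.3 makes three commitments that matter here. "All laboratory data will be listed". "Hematological, serum chemistry, coagulation assessments and their changes from baseline will be summarized", by severity grade. And "Separate listings and summaries will be prepared for laboratory abnormalities that are" Grade 3 or higher.

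SAP 7.2 opens with the data source: "Central laboratory assessment will be used for safety analysis". It then plans by-subject listings by visit "in chronological order for hematology, serum chemistry, and urinalysis separately", with flags for values outside the reference range or of Grade 1 or higher. SAP 7.2.1.2 adds a summary of baseline and worst post-baseline abnormalities for each test ("Subjects will be categorized according to the most severe post-baseline abnormality grade for a given lab test") and a second listing commitment: "A by-subject listing will include all laboratory results with flags to indicate treatment emergent laboratory abnormalities". SAP 7.2.2 adds shift tables from baseline grade to worst post-baseline grade. SAP 7.7 closes the safety section: "There are no deviations from the protocol-specified safety analyses".

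Protocol 6.2.10 requires local results that lead to a dose change to be entered on the eCRF. SAP 7.2 does not mention them.

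**The concern.** Read against protocol 8.6.3, SAP 7.2 seems to fall short in three places. It names no separate Grade 3 or higher listing or summary. Its panel listing leaves out coagulation, which in Group A is drawn repeatedly on treatment, yet it includes urinalysis, which is scheduled at screening only. It gives no place to the local values that may have driven a dosing decision. SAP 7.7 then tells the reader that nothing was changed.

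If outputs really were lost, it would matter. Safety is the primary objective, and with nine subjects the individual listings carry much of the evidence. A reader who trusted SAP 7.7 would not know to look for what was missing.

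**Working it through.** No sample size, error rate or other stated figure is involved. The check sets each protocol output beside its SAP counterpart.

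| Protocol 8.6.3 | SAP | Result |
|---|---|---|
| All laboratory data listed | Flagged listing of all results (7.2.1.2); three panels listed separately (7.2) | Present for central data |
| Hematology, chemistry and coagulation by grade, with change from baseline | Worst grade by test (7.2.1.2); normal-range frequencies where no CTCAE scale exists (7.2.1); shift tables (7.2.2) | Present; no panel excluded |
| Separate Grade 3 or higher summary | Not named | Derivable |
| Separate Grade 3 or higher listing | Not named | Subset of the full listing |

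**Grade 3 or higher.** SAP 7.2.1 grades laboratory values 0 to 4. In the worst-grade summary each subject falls in one category per test (per direction where a test is graded both ways), so the categories do not overlap:

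n(Grade 3 or higher) = n(Grade 3) + n(Grade 4), with the same denominator.

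The worst-grade summary concerns treatment-emergent abnormalities, so a value that is Grade 3 at baseline and does not worsen need not appear in it as Grade 3. The shift table covers that case, because it crosses baseline grade with worst post-baseline grade. Both counts can be read from planned tables. The individual values are in the full listing.

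**Coagulation.** SAP 7.2 says how three panels are set out. It does not limit the listing to them. SAP 7.2.1.2 asks for all laboratory results. An analyst can follow both sentences, and coagulation is then listed. The amount of data involved is as follows:

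- Protocol Table 6-1 has 3 coagulation analytes.
- A Group A subject who completes Cycle 1 and attends End of Treatment has 3 scheduled post-baseline coagulation visits (Cycle 1 Days 14 and 28, and End of Treatment; protocol 6.4.1 and 6.7).
- SAP 3 gives 9 subjects enrolled.

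3 × 3 × 9 = 81 scheduled results, if all nine were dosed and attended. Each further cycle completed by all nine adds 3 × 1 × 9 = 27. These are scheduled results, not missing ones. With SAP 7.2.1.2 in force, none is left out of the listing. Even if the three-panel sentence alone governed the listing, the by-test summary and the shift tables would still include coagulation.

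**Local results.** Protocol 8.6.3 does not mention them; the only link is its general sentence on listing all data. Protocol 6.2.10 is a rule on what goes on the eCRF. Under protocol 7.1.3 and 7.5, a laboratory abnormality that leads to interruption, modification or discontinuation of ENTO must be recorded as an adverse event. It then enters the listing of all adverse events and, if treatment-emergent, the SAP 7.1.6 tables of events leading to reduction, interruption or discontinuation. SAP 4.2.2 also lists dose modifications by subject. The documents do not say whether any dose-changing local result exists.

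**The case for a change.** The best argument for acting is that SAP 7.7 is wrong as written. The protocol promised two outputs that the SAP does not name, and early termination does not excuse this: SAP 3 cuts only efficacy to listings and keeps both tables and listings for safety. The adverse event tables are not a full substitute, since protocol 7.1.3 keeps laboratory abnormalities without clinical significance out of adverse event reporting. A symptomless Grade 3 value with no intervention or dose change would show only in laboratory output. The cut also has some bearing on this drug. Protocol 1.3.4 reports Grade 3 or higher ALT increases in 26 of 265 subjects (9.8%) in one study, and protocol 1.6.1 reports three Grade 3 transaminase elevations in another, one of them a DLT. The remedy would be cheap.

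The point about SAP 7.7 stands. The rest does not show a loss. A symptomless Grade 3 ALT value would still appear in the worst-grade row for ALT, in the shift table and in the flagged listing.

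The argument from hemorrhage monitoring in protocol 1.7.1 is weaker than it looks. The clinical pathology parameters named in that sentence do not include coagulation, and the section reports no altered coagulation in the nonclinical studies.

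For local results, what remains is that the numerical value behind a dose change may not be printed beside the central values. The event and the dose change are still reported.

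**Conclusion.** No change to the plan is needed. The inaccuracy is confined to the declaration in SAP 7.7, which overlooks two filtered presentations: one Grade 3 or higher listing and one Grade 3 or higher summary. Both are subsets of planned output, so adding them would give no count, percentage or individual value that is not otherwise available. The uneven wording on coagulation is a gap that an analyst fills sensibly by following SAP 7.2.1.2. The local-results point concerns no output named in protocol 8.6.3.

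This rests on three assumptions: SAP 7.2.1.2 is carried out as written, with coagulation treated as laboratory results; the worst-grade and shift tables show Grades 3 and 4 as separate categories; and the study stays at nine subjects on one dose level, so that the full listing can be read by eye. In a large study a filtered Grade 3 or higher listing would have practical value. Here it would save a reader a little time and leave every safety conclusion where it is.

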### **7.2.1. Graded Laboratory Values**

CTCAE Version 4.03 will be used for assigning toxicity grades (0 to 4) to laboratory results for analysis. Grade 0 includes all values that do not meet the criteria for an abnormality of at least Grade 1. For laboratory tests with criteria for both increased and decreased levels, analyses for each direction (ie, increased, decreased) will be presented separately.

For parameters for which a CTCAE scale does not exist, the frequency of subjects with values below, within, and above the normal ranges will be summarized.

#### **7.2.1.1. Treatment-Emergent Laboratory Abnormalities**

Treatment-emergent laboratory abnormalities are defined as values that increase at least 1 toxicity grade from baseline at any post-baseline time point, up to and including the date of last dose of study drug plus 30 days for subjects who permanently discontinued study drug, or the last available date in the database snapshot for subjects who were still on treatment at the time of an interim analysis. If the relevant baseline laboratory value is missing, any abnormality of at least Grade 1 observed within the time frame specified above will be considered to be treatment emergent.

#### **7.2.1.2. Summaries of Laboratory Abnormalities**

Summary (number and percentage of subjects) of baseline and worst post-baseline treatment-emergent laboratory abnormalities will be provided by lab test. Subjects will be categorized according to the most severe post-baseline abnormality grade for a given lab test.

A by-subject listing will include all laboratory results with flags to indicate treatment emergent laboratory abnormalities.

### **7.2.2. Shifts Relative to the Baseline Value**

Shift tables will be presented by showing change in severity grade from baseline to the worst post-baseline grade.

### **7.3. Body Weight and Vital Signs**

A by-subject listing of body weight and vital signs will be provided by subject ID number and visit in chronological order. High or low values for vital signs will be flagged.

### **7.4. Prior and Concomitant Medications**

Prior and concomitant medications will be coded based on World Health Organization Drug Dictionary (WHO DRUG) Version Q32017 into Anatomical-Therapeutic-Chemical classification (ATC) codes.

#### **7.4.1. Prior Medications**

Prior medications are defined as any medications taken before a subject took the first dose of study drug. For the purposes of analysis, any medication with a start date prior to the first dosing date of study drug will be considered as prior medication regardless of when the stop date is. If a partial start date is entered the medication will be considered prior unless the month and year (if day is missing) or year (if day and month are missing) of the start date are after the first dosing date. Medications with a completely missing start date will be considered as prior medication, unless otherwise specified.

#### **7.4.2. Concomitant Medications**

Concomitant medications are defined as medications taken while a subject took study drug. For the purposes of analysis, any medications with a start date prior to or on the first dosing date of study drug and continued to be taken after the first dosing date, or started after the first dosing date but prior to or on the last dosing date of study drug will be considered concomitant medications. Medications started and stopped on the same day as the first dosing date or the last dosing date of study drug will also be considered concomitant. Medications with a stop date prior to the date of first dosing date of study drug or a start date after the last dosing date of study drug will not be considered as concomitant. If a partial stop date is entered, any medication with the month and year (if day is missing) or year (if day and month are missing) prior to the date of first study drug administration will not be considered as concomitant medication. If a partial start date is entered, any medication with the month and year (if day is missing) or year (if day and month are missing) after the study drug stop date will not be considered as concomitant medication. Medications with completely missing start and stop dates will be considered as concomitant medication, unless otherwise specified.

The incomplete dates handling method used for AE summaries will be used for concomitant medication summaries (Section 7.1.5.2).

All prior and concomitant medications (other than per-protocol study drugs) will be provided in a by-subject listing sorted by subject ID number and administration date in chronological order based on FAS analysis set.

#### **7.5. Electrocardiogram and MUGA Scan**

Electrocardiogram (ECG) and MUGA data will not be presented in the synoptic CSR since ECGs and MUGA scan were not assessed in this study other than as part of the screening process for potential new subjects.

#### **7.6. Other Safety Measures**

No additional safety measures are specified in the protocol.

#### **7.7. Changes From Protocol-Specified Safety Analyses**

There are no deviations from the protocol-specified safety analyses.

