#### **8.1.2. Primary Endpoints**

The primary endpoints of this study are:

Safety Endpoints:

- Occurrence of AEs and laboratory abnormalities defined as DLTs for ENTO monotherapy in subjects with relapsed or refractory hematologic malignancies
- Occurrence of AEs and laboratory abnormalities defined as DLTs for ENTO in combination with cytarabine and daunorubicin in subjects with previously untreated AML who are candidates for chemotherapy

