## **8.3. Data Handling Conventions**

By-subject listings will be created for important variables from each eCRF module. Summary tables for continuous variables will contain the following statistics: N (the number of subject in group), n (the number of subjects with assessment), mean, standard deviation, 95% confidence intervals (CIs) on the mean, median, minimum, and maximum. Summary tables for categorical variables will include: N, n, percentage, and 95% CIs on the percentage. Unless otherwise indicated, 95% CIs for binary variables will be calculated using the binomial distribution (exact method) and will be 2-sided. Data will be described and summarized by dose level, analysis set, and timepoint. As appropriate, changes from baseline to each subsequent timepoint will be described and summarized. Similarly, as appropriate, the best change from baseline during the study will also be described and summarized. Graphical techniques (eg, waterfall plots, Kaplan-Meier curves, line plots) may be used when such methods are appropriate and informative.

The baseline value used in each analysis will be the last (most recent) pre-treatment value. Data from all sites will be pooled for all analyses. Analyses will be based upon the observed data unless methods for handling missing data are specified. If there is a significant degree of non-normality, analyses may be performed on log-transformed data or nonparametric tests may be applied, as appropriate.

Unless otherwise specified, all analyses will be 2-sided at the 0.05 level of significance.

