### **8.6.1. Extent of Exposure**

Descriptive information will be provided by phase and dose level regarding the number of doses of study treatment prescribed the total number of doses taken, duration of treatment, and the number of prescribed dose reductions and interruptions.

ENTO compliance will be described in terms of the proportion of study treatment actually taken based on returned pill count relative to the amount that was dispensed (taking into account physician-prescribed reductions and interruptions).

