### **8.6.2. Adverse Events**

All AEs will be listed. The AE summarization will focus on treatment-emergent AEs. Treatment-emergent AEs are defined as AEs that onset in the period from the first dose of study treatment to 30 days after the permanent discontinuation of study treatment or that lead to permanent study treatment discontinuation.

AEs that occur before the first dose of study treatment or >30 days after study treatment discontinuation will be included in data listings.

AEs will be classified using Medical Dictionary for Regulatory Activities (MedDRA) with descriptions by System Organ Class, High-Level Group Term, High Level Term, Preferred Term, and Lower-Level Term. The severity of AEs will be graded by the investigator according to the CTCAE, Version 4.03 (<http://www.hrc.govt.nz/sites/default/files/CTCAE%20manual%20-%20DMCC.pdf>), whenever possible. If a CTCAE criterion does not exist for a specific type of AE, the grade corresponding to the appropriate adjective will be used by the investigator to describe the maximum intensity of the AE: Grade 1 (mild), Grade 2 (moderate), Grade 3 (severe), Grade 4 (life threatening), or Grade 5 (fatal). The relationship of the AE to study treatment will be categorized as related or unrelated.

Treatment-emergent AEs will be summarized by presenting the number and percentage of subjects with treatment-emergent AEs by severity grade. Subjects who report multiple treatment-emergent AEs under the same Preferred Term (or System Organ Class) are counted only once under the worst severity grade. The summary will be presented in decreasing frequency of System Organ Class and Preferred Term of the 'Total' column. Within the same frequency, the AEs are ordered in the alphabetical order of System Organ Class and Preferred Term. Separate listings and summaries will be provided for the following types of treatment-emergent AEs:

- Study treatment related AEs
- AEs with severity  $\geq$  Grade 3
- AEs leading to study treatment interruption and/or dose modification
- AEs leading to study treatment discontinuation
- Study treatment related SAEs
- DLT
- DLT rates and their 90% CI

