##### **3.1.2. Dose-Limiting Toxicity (DLT) Analysis Set**

DLT Analysis Set includes all subjects in the FAS who meet at least one of the following criteria:

- Receive at least 21 days of ENTO during the DLT assessment window (refer to Section 1.2).
- Experience a DLT during the DLT assessment window.

This analysis set will be used for analyses related to DLT.

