## **4. SUBJECT DISPOSITION**

### **4.1. Subject Enrollment and Disposition**

A summary of subject disposition will be provided by dose level based on FAS. This summary will present the number and percentage of subjects in the following categories:

- ENTO discontinuation
  - Reasons of ENTO discontinuation
- Included in the DLT analysis set
- Study discontinuation
  - Reasons of Study discontinuation

The denominator for the percentage calculation will be the total number of subjects in FAS corresponding to that column.

A data listing of subject enrollment to describe the site, subject number, date of first and last dose and dose level of ENTO, analysis set inclusion (FAS and DLT analysis sets), reasons for ENTO discontinuation, and reasons for study discontinuation will be provided.

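### The SAP drops the protocol's DLT rate and 90% confidence interval for the primary endpoint, yet SAP 7.7 says no safety analysis has changed

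*SAP*

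**What the plan says.** Protocol 8.1.2 gives the Group A primary endpoint as "Occurrence of AEs and laboratory abnormalities defined as DLTs for ENTO monotherapy". Protocol 8.6.2 promises both listings and summaries for a set of adverse-event categories. The last two entries are DLT and, as a separate item, "DLT rates and their 90% CI". Protocol 8.3 sets the default interval method: unless stated otherwise, "95% CIs for binary variables will be calculated using the binomial distribution (exact method) and will be 2-sided". Section 8.6.2 therefore changes the level to 90% for DLT rates and is silent on the method.

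The SAP defines a DLT Analysis Set in 3.1.2 and says of it: "This analysis set will be used for analyses related to DLT". The only DLT output it then names is in 7.1.7: "A listing of the DLT AEs will be provided by dose level". The disposition table in SAP 4.1 includes a row "Included in the DLT analysis set". SAP 7.7, the section for declaring changes to safety analyses, reads: "There are no deviations from the protocol-specified safety analyses".

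On compliance, protocol 8.6.1, which sits under Safety Analysis, says "ENTO compliance will be described in terms of the proportion of study treatment actually taken", based on pill counts. SAP 4.2.2 provides a by-subject listing of drug accountability and dose modification.

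**The concern.** A listing can meet the protocol's DLT item. It cannot meet the separate item for a rate with its interval. If the SAP is followed as written, the synoptic CSR will report the primary endpoint without the summary the protocol planned for it, and SAP 7.7 will support a statement that nothing was changed. If no DLT occurred, the listing would be empty and the report would give no figure at all for how high the DLT rate could still be.

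The stakes are limited. SAP 1.3 says there is no formal hypothesis, Group B will not open, and SAP 1 says the termination was not for safety reasons. No dose or enrolment decision depends on the interval. What is at stake is whether the primary endpoint is reported as planned, and whether the record of changes is true.

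**Working it through.** **Step 1: compare the protocol requirement with the SAP.**

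| Place | What it provides for DLT |
|---|---|
| Protocol 8.6.2 | Listing and summary of DLTs; DLT rate with 90% interval |
| SAP 3 | General rule that safety gets both tables and listings; DLT not mentioned |
| SAP 4.1 | Count of subjects in the DLT Analysis Set, not of subjects with a DLT |
| SAP 7.1.6 | Adverse-event summaries; no DLT entry |
| SAP 7.1.7 | Analysis population named; the only output is a listing of DLT events |
| SAP 7.7 | States that nothing was changed |

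No row from the SAP contains a DLT rate, a confidence level or an interval method. Redaction does not explain this: the blacked-out SAP text is in 6.3 (exploratory efficacy), and 7.1.6, 7.1.7 and 7.7 are readable. Early termination does not explain it either, because SAP 3 reduces only efficacy to listings and keeps tables for safety.

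**Step 2: what could be recovered.** The numerator (subjects with a DLT) can be counted from the 7.1.7 listing, and the denominator is the 4.1 count. The reported rate and its precision are what is missing.

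**Step 3: what the omitted analysis would show.** The plan states no DLT rate or interval, so there is no figure to reproduce. Inputs:

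- Subjects enrolled: 9 (SAP 3).
- Evaluable subjects in the design: 6 at dose level 0 (protocol 8.8; SAP 1.3).
- Confidence level: 90% (protocol 8.6.2).
- Method: exact binomial, two-sided, inferred from the protocol 8.3 default.
- Final number evaluable (n) and number with a DLT (x): not given. The values n = 6 to 9 and x = 0 to 2 are assumptions.

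Clopper-Pearson limits: lower = Beta quantile at 0.05 with parameters (x, n − x + 1), taken as 0 when x = 0; upper = Beta quantile at 0.95 with parameters (x + 1, n − x). For x = 0 the upper limit reduces to 1 − 0.05^(1/n). With n = 6 this is 1 − 0.607 = 0.393, and with n = 9 it is 1 − 0.717 = 0.283.

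| n | 0 DLTs | 1 DLT | 2 DLTs |
|---|---|---|---|
| 6 | 0% (0 to 39.3%) | 16.7% (0.9 to 58.2%) | 33.3% (6.3 to 72.9%) |
| 7 | 0% (0 to 34.8%) | 14.3% (0.7 to 52.1%) | 28.6% (5.3 to 65.9%) |
| 8 | 0% (0 to 31.2%) | 12.5% (0.6 to 47.1%) | 25.0% (4.6 to 60.0%) |
| 9 | 0% (0 to 28.3%) | 11.1% (0.6 to 42.9%) | 22.2% (4.1 to 55.0%) |

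The column for two DLTs is included because the documents do not exclude it. SAP 3.2 attributes the single dose level to early termination, so the absence of dose level -1 does not show that at most one DLT occurred.

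**Step 4: compliance.** SAP 4.2 says in general terms that the level of adherence will be assessed and that summaries use the FAS. Neither 4.2 nor 4.2.2 gives the pill-count proportion of protocol 8.6.1; the only adherence output named is the accountability and dose-modification listing.

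**The case against.** The strongest case is that the consequence is small. The primary endpoint is worded as occurrence, and a listing by subject together with the size of the DLT Analysis Set reports occurrence in full. With nine subjects, any reader can form the rate and an exact interval. The SAP openly describes an early termination and a synoptic report, and protocol 9.2.2 allows an abbreviated report. SAP 3 retains safety tables, and 7.1.7 says DLT will be analysed before it names the listing, which leaves room for a summary table.

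The point about consequence stands: this is a reporting gap, not a threat to the study's validity. The rest does not close the gap. The protocol asked for a reported rate with its precision, and a general promise of safety tables supplies neither a DLT rate nor a confidence level or method. The description of the reduced scope does not mention the DLT rate. If early termination were the reason for dropping it, SAP 7.7 would be the place to say so.

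On compliance, it can be argued that SAP 4.2 already promises an adherence summary, and that 7.7 covers only SAP Section 7, whereas adherence sits in Section 4. This weakens the example without removing it: the protocol classes compliance under Safety Analysis, and its proportion appears nowhere in the SAP. It is secondary, and the main point does not rest on it.

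**Conclusion.** The concern holds. The protocol requires a DLT rate with a 90% interval, the SAP provides only a listing, and the no-change statement in SAP 7.7 is therefore inaccurate. The analysis is feasible and its imprecision is worth showing: with no DLTs, the upper 90% limit would still be between 28.3% (9 evaluable) and 39.3% (6 evaluable). These figures rest on assumed counts and on the exact method being the one intended. The matter should be corrected before the report is written, but it affects the completeness and accuracy of reporting only.

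**What to change.** - In SAP 7.1.7, add one table on the DLT Analysis Set: number evaluable, number and percentage with at least one DLT, and a two-sided 90% confidence interval. State that the interval is exact binomial (Clopper-Pearson), because protocol 8.6.2 gives the level but not the method.
- Replace the sentence in SAP 7.7 with a list of the protocol safety analyses that remain dropped or changed, each with its reason. The pill-count compliance proportion belongs there unless it is restored in SAP 4.2.2.
- If the sponsor decides not to report the DLT rate and interval, declare and justify that omission in SAP 7.7.

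The cost is SAP wording and one small table from data already collected.
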